6.3 Trial treatment period

- The trial treatment period begins on the day of starting the trial drug. Treatment should start within 3 calendar days of randomisation and will continue for 2 years or until disease progression, death, unacceptable toxicity, or withdrawal of patient consent for data transfer
- For the purposes of pharmacovigilance reporting the end of the trial treatment period is 28 days after the final dose of trial drug has been taken

6.4 Restrictions during the trial

6.4.1 Contraception

Patients of child bearing potential (female patients who have experienced menarche, are not post-menopausal and have not been permanently sterilised) and their partners, who are sexually active, must agree to the use of two highly effective forms of contraception throughout their participation in the trial and for 3 months after last dose of trial drug:

- Condom with spermicide

and one of the following:

- Oral contraceptive or
- Hormonal therapy (e.g. hormone implants) or
- Placement of an intra-uterine device

STOMP Protocol

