5.2 Patient eligibility

5.2.1 Inclusion Criteria

1. Pathologically confirmed SCLC (M0 or M1a/b with any T or N stage), please see Appendix 1 for the AJCC TNM staging for lung cancer
2. Completed ≥ 3 cycles of first line chemotherapy or chemo-radiotherapy with cisplatin + etoposide or carboplatin + etoposide
3. Complete Response (CR) or Partial Response (PR) to first line chemotherapy (Response Evaluation Criteria in Solid Tumours [RECIST] 1.1 – see Appendix 3)
4. Eastern Co-operative Oncology Group (ECOG) (see Appendix 2) performance status 0-2, and a life expectancy of greater than 12 weeks
5. Resolution of all previous chemotherapy toxicity (except alopecia) to grade 1 or better
6. Adequate physiological function:
Calculated or measured creatinine clearance ≥ 50 ml/min (Cockcroft-Gault) and serum creatinine ≤ 1.5 x institutional upper limit of normal (ULN), Haemoglobin (Hb) ≥ 100 g/L, white blood cells (WBC) $\geq 3 \times 10^9$ /L, absolute neutrophil count (ANC) $\geq 1.5 \times 10^9$ /L, platelet count $\geq 100 \times 10^9$ /L, aspartate aminotransferase (AST) or alanine transaminase (ALT) ≤ 2.5 x institutional ULN unless liver metastases are present in which case it must be ≤ 5 x ULN, total bilirubin ≤ 1.5 x institutional ULN
7. Negative pregnancy test (for female patients of child-bearing potential)
8. Agrees to comply with contraceptive measures as per Section 6.4.1
9. Provision of written informed consent
10. Able to swallow oral medication
11. Patient is willing and able to comply with the protocol for the duration of the trial including undergoing treatment and scheduled visits and examinations

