5.2.2 Exclusion Criteria

1. Age ≤ 18 years
2. Interval from last anticancer treatment to start of trial treatment:
 - o last radiotherapy fraction > 21 days*
 - o start of final cycle of chemotherapy > 42 days*
 - o radiotherapy must begin within 35 days of the start of the last chemotherapy cycle

STOMP Protocol

- * If sequential chemotherapy then radiotherapy then apply the interval for the last radiotherapy fraction. If concurrent chemotherapy and radiotherapy then ensure the trial treatment start date is within whichever is the later interval.
- 3. Patients with symptomatic uncontrolled brain metastases. A scan to confirm the absence of brain metastases is not required. The patient can receive a stable dose of corticosteroids before and during the trial as long as these were started at least 28 days prior to trial treatment
- 4. Interstitial lung disease
- 5. Previous malignancies (except curatively treated non-melanoma skin cancer or carcinoma *in situ* of the cervix or breast) within the past 3 years
- 6. History of malabsorption or major gastrointestinal tract resection likely to affect trial drug absorption
- 7. Treatment with any investigational product during the last 14 days (or a longer period depending on the defined characteristics of the agents used)
- 8. Any previous treatment with a PARP inhibitor, including olaparib
- 9. Patients receiving the following classes of inhibitors of CYP3A4 (see Section 6.4.2 for guidelines and wash out periods): azole antifungals, macrolide antibiotics, protease inhibitors
- 10. Patients considered a poor medical risk due to a serious, uncontrolled medical disorder, non-malignant systemic disease or active, uncontrolled infection. Examples include, but are not limited to, uncontrolled ventricular arrhythmia, recent (within 3 months) myocardial infarction, uncontrolled major seizure disorder, unstable spinal cord compression, superior vena cava syndrome, or any psychiatric disorder that prohibits obtaining informed consent
- 11. Breast feeding women
- 12. Immunocompromised patients, e.g. patients who are known to be serologically positive for human immunodeficiency virus (HIV)
- 13. Patients with known active hepatic disease (i.e., Hepatitis B or C)
- 14. Patients with a known hypersensitivity to olaparib or any of the excipients of the product
- 15. Patients with uncontrolled seizures
- 16. Patients with myelodysplastic syndrome (MDS) / acute myeloid leukaemia (AML)

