7.1.7 Follow-up Assessments

Patient should be followed up as detailed in Section 6.5. A Follow-up Form should be completed every 3 months for all patients following discontinuation of treatment (unless patient has withdrawn consent for future data transfer). Patients who discontinue treatment for reasons other than progression should continue to have CT scans every 8 weeks until progression, or alternatively until the follow-up period of the trial is complete. A Response Form should therefore be completed every 8 weeks for these patients.

Archival tumour tissue samples will be requested retrospectively during the follow-up period (see Section 9).

STOMP Protocol

Table 7.1 Schema of trial assessments

	Screening (Day -28 to 0)	Pre-cycle 1 (Day -7 to treatment commence- ment)	Cycle 2 and all subsequent cycles (Day 1 of 4 weekly visit)	End of odd cycles ⁱ	End of even cycles ^j	Treatment dis- continuation (28 days post completion of treatment)	Follow- up ^l
Informed consent	X						
Medical history	X						
Review of Inclusion/exclusion criteria	X						
Peripheral blood smear to test for MDS & AML (if clinically indicated)	X						
Physical examination	X	X	X				
Vital signs, body weight (includes BP, pulse and temperature) Height only at screening	X	X	X				
ECOG performance status	X	X	X				
Haematology ^a / clinical chemistry ^b	X	X	X			X	
Pregnancy test ^c	X						
Coagulation tests (if clinically indicated) ^{d+e}	X		X				
Blood sample for biomarker analysis & CTC		X	X ^h			X	
Tumour Assessment (CT according to RECIST)	X				X ^k		X ^m
Chest X-ray ^f		X		X			
Patient Diary		X	X				
Quality of Life Questionnaire (EQ- 5D-3L)		X	X			X	
Adverse Events	X		X			X	
Concomitant medications	X		X			X	
Randomisation (day 0 only)	X						
Olaparib/placebo dispensed/returned		X ^g	X				
Archival tumour sample (when available)							X
Survival							X

a Haematology to include Hb, WBC, ANC, platelets.

b Clinical chemistry to include calculated or measured creatinine clearance, AST/ALT and total bilirubin at screening and sodium, potassium, adjusted calcium, urea, creatinine, albumin, total serum protein, total bilirubin, alkaline phosphatase, AST/ALT at all other time points.

c For female patients of child-bearing potential as defined in Section 6.4.1.

d Coagulation test to include INR and APTT.

STOMP Protocol

- e Recommended during treatment if patient is receiving warfarin, measured weekly for first month and monthly thereafter.

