10.1.3 Monitoring Pregnancies for Potential Serious Adverse Events

It is important to monitor the outcome of pregnancies of patients in order to provide SAE data on congenital anomalies or birth defects.

In the event that a patient or their partner becomes pregnant during the SAE reporting period please complete a Pregnancy Notification Form (providing the patient's details) and return to the STOMP Trial Office as soon as possible. If it is the patient who is pregnant provide outcome data on a follow-up Pregnancy Notification Form. Where the patient's partner is pregnant consent must first be obtained and the patient should be given a Release of Medical Information Form to give to their partner. If the partner is happy to provide information on the outcome of their pregnancy they should sign the Release of Medical Information Form. Once consent has been obtained provide details of the outcome of the pregnancy on a follow-up Pregnancy Notification Form. If appropriate also complete an SAE Form as detailed below.

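### Section 6.4.1 confines the contraception rule to female patients and their partners, so inclusion criterion 8 places no duty on male patients, who are eligible

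*Protocol*

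**What the plan says.** Protocol section 6.4.1 sets the contraception rule. The people bound are "Patients of child bearing potential (female patients who have experienced menarche, are not post-menopausal and have not been permanently sterilised) and their partners", if sexually active. They must use two methods in combination: "Condom with spermicide", plus an oral contraceptive, another hormonal method or an intra-uterine device. The duty runs "throughout their participation in the trial and for 3 months after last dose of trial drug".

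Inclusion criterion 8 (section 5.2.1) turns this into an entry condition: "Agrees to comply with contraceptive measures as per Section 6.4.1". It adds no content of its own.

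Footnote c of Table 7.1, on the pregnancy test, relies on the same definition: "For female patients of child-bearing potential as defined in Section 6.4.1".

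Section 10.1.3 deals with pregnancies that occur on the trial: "In the event that a patient or their partner becomes pregnant during the SAE reporting period please complete a Pregnancy Notification Form". It gives a pregnant partner a separate consent and release-form route. Its stated aim is to capture congenital anomalies and birth defects.

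**The concern.** The protocol foresees that a patient's partner may become pregnant and wants the outcome of that pregnancy. In practice this route serves the female partners of male patients. Yet the rule meant to prevent pregnancy during treatment does not reach those men. A site that applies the protocol to the letter asks a woman of child-bearing potential for two methods and asks nothing of a man whose partner could conceive.

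A precaution for men would be reasonable on the protocol's own description of the drug. Section 1.2 describes PARP proteins as serving DNA repair and genomic integrity, olaparib inhibits them, and section 6.1 allows continuous dosing for up to 2 years. Any consequence would fall on a partner and fetus outside the trial. The protocol gives no reason for leaving men out.

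**Working it through.** No formula or stated figure is involved. The check sets the relevant sections side by side.

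1. **Whom does 6.4.1 bind?** The definition in brackets makes the patients concerned female. The partners mentioned belong to those patients. Two groups result: female patients of child-bearing potential, and those women's partners. A male patient with a female partner is in neither.

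2. **Is that reading confirmed elsewhere?** Yes. Table 7.1 footnote c treats 6.4.1 as the place where female patients of child-bearing potential are defined.

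3. **Can men enter the trial?** Yes, by implication. No criterion in 5.2.1 or 5.2.2 restricts sex, and the screening log in 5.3.1 records gender. Where a criterion concerns women only, the protocol says so: inclusion criterion 7 reads "Negative pregnancy test (for female patients of child-bearing potential" and exclusion criterion 11 reads "Breast feeding women".

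4. **What does inclusion criterion 8 ask of a man?** It carries no sex limit, so on its face it applies to him. Its only content is 6.4.1, which does not cover him. The duty is empty.

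5. **Is there another rule for men?** None appears in the supplied protocol. Section 6.4.1 itself is complete, with no text blacked out.

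6. **Does the protocol expect partner pregnancies?** Yes, in 10.1.3.

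7. **How many men are affected?** This cannot be derived. The protocol gives neither the expected sex ratio nor the share of men with a partner who could conceive. It gives only the totals:
   - Target recruitment is 225 (section 15.3) and allocation is 2:1:2:1 (section 5.4).
   - Olaparib: 225 × 4/6 = 150. Placebo: 225 × 2/6 = 75.
   - Each percentage point of such men among those recruited would be 225 × 0.01 = 2.25 patients, of whom 150 × 0.01 = 1.5 would be on olaparib.
   - The share itself is unknown, so this gives a scale and not an estimate. Because treatment is blinded, any rule would have to cover both arms.

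**The case against.** The strongest reply is that the documents give no reason why men need contraception. Section 1.4 names the bone marrow as the target organ of toxicity and refers to the Investigator's Brochure for the rest. If the Brochure supports no male requirement, limiting the rule to women is a defensible choice. That source is not available here, so the point stands as an incomplete precaution only. A reader might infer that partners of men on olaparib are shown to be at risk. The protocol contains no male reproductive data, so that inference is not supported.

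A reader might also see a contradiction between 6.4.1 and 10.1.3. There is none. Collecting pregnancy outcomes is compatible with having no preventive rule, and 10.1.3 shows only that partner pregnancies were foreseen.

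A third tempting inference is that men in the trial receive no contraceptive advice. The patient information sheet and the Brochure may well give some. What can be shown is narrower: criterion 8 cites 6.4.1 alone, and 6.4.1 leaves men out.

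Finally, loose drafting is plausible. A condom combined with a method used by the woman would suit a couple whichever of them is the patient, and the bracketed definition also serves the pregnancy test. The drafters may have meant to cover men. If so, the text still needs correcting, because the definition as written rules that reading out.

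**Conclusion.** The point holds as a gap in the scope of a safety rule. Read as written, 6.4.1 and inclusion criterion 8 place no contraception duty on male patients, while men are eligible and partner pregnancies are to be followed for birth defects.

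The conclusion rests on two things: male eligibility, which is inferred from the absence of any sex restriction and from the explicit female-only wording elsewhere, and the absence of any other contraception rule in the supplied text. The number of men concerned cannot be estimated. That it is probably small is a judgement, not a figure from the protocol. Sample size, blinding and analysis are unaffected. Minor severity; a cheap improvement.

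**What to change.** Extend section 6.4.1 to sexually active male patients who are not permanently sterilised and whose partner is of child-bearing potential. Require condom use by the patient, as the section already specifies, plus one of the listed second methods for the partner. Apply the period already set for women: the whole time on trial and the 3 months following the final dose.

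Before adopting this, check it against the Investigator's Brochure and depart from it only if the Brochure supports a different requirement for men. The two-method rule and the 3-month period are carried over from the women's rule, since the protocol offers no male data for either. The sterilisation exemption mirrors the one that women already have.

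Inclusion criterion 8 would then cover these men without rewording. Align the patient information sheet if it differs.

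The cost is a short amendment and a small restriction on some men, including those on placebo because allocation is blinded. Part of the burden falls on their partners, who are not trial participants and would be the ones using the second method.

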6.4.2 Concomitant Therapy

Please refer to the Investigator Brochure for all known contraindications for olaparib.

The use of any natural/herbal products or other “folk remedies” should be discouraged but use of these products, as well as use of all vitamins, nutritional supplements and all other concomitant medications must be recorded on the Concomitant Medication Log.

6.4.3 Olaparib and CYP3A4

Olaparib is an investigational drug for which no data on *in vivo* interactions are currently available. Based on *in vitro* data and clinical exposure data, olaparib is considered unlikely to cause clinically significant drug interactions through inhibition or induction of cytochrome P450 enzyme activity. *In vitro* data have, however, also shown that the principal enzyme responsible for the formation of the three main metabolites of olaparib is CYP3A4 and consequently, although the contribution of metabolic clearance to total drug clearance in man is currently unknown, to ensure patient safety, the following potent inhibitors of CYP3A4 must not be used during this trial for any patient receiving olaparib.

While this is not an exhaustive list, it covers the known potent inhibitors, which have most often previously been reported to be associated with clinically significant drug interactions:

- ketoconazole, itraconazole, ritonavir, indinavir, saquinavir, telithromycin, clarithromycin and nelfanvir

For patients taking any of the above, the required wash-out periods prior to starting olaparib/placebo is one week.

In addition, to avoid potential reductions in exposure due to drug interactions, the following CYP3A4 inducers should be avoided:

- Phenytoin, rifampicin, rifapentin, rifabutin, carbamazepine, phenobarbitone, nevirapine, modafinil and St John’s Wort (*Hypericum perforatum*)

For patients taking any of the above, the required wash-out periods prior to starting olaparib/placebo are:

- phenobarbitone 5 weeks, and
- for any of the others, 3 weeks

After randomisation if the use of any potent inducers or inhibitors of CYP3A4 are considered necessary for the patient’s safety and welfare, the Investigator must contact the STOMP Trial Office for referral to the Chief Investigator. A decision to allow the patient to continue in the trial will be made on a case-by-case basis.

6.4.4 Other Concomitant Medications

Medications (prescriptions or over-the-counter medications) continued at the start of the trial or started during the trial or until 28 days from the end of the last protocol treatment and different from the trial medication must be documented. This includes any medications, with the exceptions noted in Section 6.4.2, which are considered necessary for the patient's welfare, and which it is believed will not interfere with the trial medication. These may be given at the discretion of the Investigator, providing the medications, the doses, dates and reasons for administration are recorded on the relevant CRF.

STOMP Protocol

Live Vaccines: Live virus and bacterial vaccines should not be administered whilst the patient is receiving trial medication and during the 28 day follow up period. An increased risk of infection by the administration of live virus and bacterial vaccines has been observed with conventional chemotherapy drugs and the effects with olaparib are unknown. Other routine vaccinations, e.g. for seasonal influenza are permitted.

Anticoagulant Therapy: Patients who are taking warfarin may participate in this trial; however, it is recommended that prothrombin time (INR and APTT) be monitored carefully at least once per week for the first month, then monthly if the INR is stable. Subcutaneous heparin is permitted.

Anti-emetics/Anti-diarrhoeals: Prophylactic anti-emetics and/or anti-diarrhoeals will not routinely be given. Should a patient develop nausea, vomiting and/or diarrhoea, which, in the Investigator's opinion, is considered related to the trial medication, then appropriate prophylactic treatment may be given.

The reason(s) for the use, doses and dates of treatment should be recorded in the patient's medical records and appropriate section of the relevant CRF.

6.4.5 Palliative Radiotherapy

Palliative radiotherapy may be used for the treatment of pain at the site of bony metastases that were present at baseline, provided the Investigator does not feel that these are indicative of clinical disease progression during the trial period. Trial drug interruption is not required (Section 6.2).

6.4.6 Administration of Other Anti-cancer Agents

Patients must not receive any other concurrent anti-cancer therapy, including investigational agents, while on trial treatment. Patients may continue the use of bisphosphonates for bone disease and corticosteroids provided the dose is stable before and during the trial and they were started at least 4 weeks prior to beginning trial treatment. Short courses of corticosteroids can be given if clinically indicated for acute exacerbations of chronic obstructive pulmonary disease.

6.5 Follow up period

Patient follow-up will continue until 2 ½ years after the last patient has been recruited.

Patients who discontinue treatment for reasons other than progression should continue to have CT scans every 8 weeks until progression or alternatively until the follow-up period is complete.

The frequency of follow-up for patients, after the treatment phase has ended, will be at the discretion of the Investigator at the recruiting sites. It is anticipated that patients will be seen as a minimum every three months.

A Follow-up Form should be completed by the Investigator or a delegated member of the site research team and returned to the STOMP Trial Office every three months until the patient dies or the end of the follow-up period as defined above. This form will capture the date the patient was last seen in that 3 month follow-up period.

Every endeavour should be made to follow patients up in accordance with the protocol. Where patients fail to attend clinic the patient's GP should be contacted for follow-up information, patient consent permitting.

6.6 Definition and recording of recurrence and disease progression

Disease progression is defined by RECIST (v1.1) as an increase by 20% in the sum of tumour diameters for target lesions, or the appearance of new lesions, taking as reference the smallest sum of tumour diameters since randomisation (including the baseline sum) or the unequivocal progression of non-target lesions.

Recurrence is defined as clinical or radiological progression of disease from remission status at trial entry (CR or PR).

Details of all recurrences must be included on the CRF along with their subsequent clinical response.

6.7 Translational studies

The translational studies are an intrinsic part of the STOMP trial and include blood and tumour sample collection. Consent for these optional studies will be obtained. Refusal of patients to consent to tissue sample collection will not exclude them from participating in the rest of the trial.

See Section 9 for more details.

7.0 TRIAL ASSESSMENTS

7.1 Assessment schedule

See Scheme of Trial Assessments (see Table 7.1).

Assessment will be timed in weeks or months from randomisation unless specified.

7.1.1 Screening (day -28 to 0, i.e. Randomisation Date)

The following assessments should be performed to assess eligibility during the screening period:

- Medical history including AE review (from time of consent) and concomitant medication review
- Physical examination (including height and weight) to assess fitness and ECOG performance status
- Blood pressure (supine), pulse and temperature
- The following tests should be conducted to confirm patient eligibility:
 - Hb
 - WBC
 - ANC
 - Platelet count
 - Calculated or measured creatinine clearance
 - AST/ALT
 - Total bilirubin
- Coagulation tests (APTT and INR) if clinically indicated (unless the patient is receiving warfarin)
- Peripheral blood smear to test for MDS and AML (if clinically indicated)
- Pregnancy test for female patients of child-bearing potential (see Section 6.4.1)

STOMP Protocol

- CT chest and upper abdomen (to include liver and adrenals) performed in accordance with RECIST 1.1 (see Appendix 3)
- Final confirmation of eligibility (at point of randomisation)

